Initially two cohorts of 10 patients with positive lymph nodes (as verified on postoperative histology) will be treated with different doses of 5-ALA. As lymph nodes can only be verified on post-operative histology it is anticipated that up to 16 patients may need to be treated to identify 10 with positive lymph nodes. As previously stated, we will attempt to enrich the study population to contain patients

Page | 31

with lymph node disease, but it is emphasised that this cannot be done accurately on preoperative CT staging. As a result, more than 10 patients may have to be recruited to each cohort to achieve the required 10 with positive lymph node disease. Sixteen patients per cohort have been anticipated as there is only 25% -30% lymph node positivity in colorectal cancer. With enrichment of recruitment, to include more lymph node positive patients using the FOxTROT radiology criteria, we estimate that 10 out of 16 patients will be informative with positive lymph nodes. In patients without lymph node disease, fluorescence of the primary cancer will act as a positive control of efficacy of 5-ALA FD of colorectal cancer. Table 1 below provides a guide to the doses that may be used. The two participating centres will work together in this regard, so as to co-ordinate between themselves, but the exact dose administered to each patient will be at the discretion of the treating surgeon. We will start with the predicted optimal dose of administration i.e. 20mg/kg (the most commonly used dose and timing in the literature – Appendix 1). A second cohort will be assessed at a lower dose of 10mg/kg if 20mg gives an indication of activity, or a higher dose of 30mg/kg if 20mg/kg does not give adequate indication of activity. In this way, by the time we have recruited 20 patients with positive lymph nodes we will have optimised the dose of administration.

Tabl	e 1
------	-----

Schedule	5-ALA dose
Cohort 1	20 mg/kg
Cohort 2	10 mg/kg or 30 mg/kg depending on activity
	of 5-ALA at 20 mg/kg

Information will be collected for each dose level including

- toxicity
- 5-ALA identified LN
- Histopathologically confirmed LN status

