13.4 Operative assessments and data collection

An operative CRF will be completed. This will collate data relating to the operation including:

Surgeon

ASA status

Details of D-Light 5-ALA lymph node assessment

Settings of Storz D-light laparoscopic system for 5-ALA fluorescence detection Type of operation performed

Whether outcome of operation curative, palliative or unresectable in the opinion of the surgeon at the time of operation

Type of anastomosis

Any intra-operative complications, including open conversion

As patients will be undergoing cancer operations, it will not be possible to blind the surgeon to the result of the preoperative CT scan. The preoperative CT scan is fundamental to selection of the patient for curative surgery.

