15. ENDPOINTS

15.1 Primary Endpoints

 Identification of the optimal dose for oral administration of 5-ALA for the accurate intraoperative detection of lymph node metastases

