15.2 Secondary Endpoints

- Standardisation of preoperative CT reporting, with emphasis on lymph node evaluation
- Standardisation of operative procedure including D3 lymphadenectomy
- Optimisation and standardisation of fluorescence detection system.
- Standardisation of pathological lymph node mapping and step sectioning for in depth lymph node evaluation.
- Patient factors affecting the accuracy of 5-ALA fluorescence diagnosis.
- Safety

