Appendix 4: Surgical proforma

Introduction

The guidance below is provided with the aim of establishing a standard surgical procedure with regards to documentation of areas of fluorescence and extent of dissection and resection.

Operative assessment

The surgeon's details will be documented along with the patient's ASA.

The dosage and timing of administration of 5-ALA will be noted prior to initial laparoscopy, thus compiling a set of data to optimise the protocol during the evaluation phase. The settings of the Storz D-light laparoscopic system for 5-ALA fluorescence detection will also be documented.

The method of establishing pneumoperitonum and port site location and size will be performed according to the surgeon's preference.

Participants will undergo initial laparoscopic assessment to identify the overall lymphatic anatomy (colorimetric dye) and the presence of fluorescence (5-ALA) of lymph nodes, tumour and any additional areas within the parietal or visceral peritoneum.

Fluorescent lymph nodes will be marked with ligaclips to facilitate subsequent pathological identification.

The estimated location of the tumour and position of any fluorescent nodes (D1/D2/D3), including their size and number will be marked on the diagram (modified Japanese sub-group classification of nodal stations) in figure 1 and noted on table 1. The anatomy of the right colic artery will be noted on figure 2. Any anomalies involving a left sided resection will be noted on figure 3. Any additional areas of fluorescence; size, approximate location and whether excised as separate specimen will be noted on table 1.

Photos and videos will be taken via the laparoscopic stack to document areas of fluorescence.

Following initial laparoscopy patients will undergo segmental colectomy with D3 lymphadenectomy. A note will be made of the type of operation performed.

Right Hemicolectomy

For cancers of the right colon (caecum to the medial border of the falciform ligament) segmental colectomy with D3 lymphadenectomy will include:

- Incision of the mesocolon at the root of the ileocolic vessels, extending towards the planned site of terminal ileal division.
- Medial to lateral dissection in the retroperitoneal plane with ventral displacement of the right ureter and duodenum. Proximal dissection of the ileocolic vessels to their superior mesenteric origin.
- High, central ligation of ileocolic artery and vein

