Station number 11	Vessel	Node	Estimate size of node (mm)	Comments e.g. Apical node	Colorimetric dyevisible Yes/No	Fluorescent Yes/no
21	D1 Ileocolic D2	2 1 2				
31	lleocolic D3	1 2		e.g.Apical (ileocolic)		
12	Right colic D1	1 2				
22	Right Colic D2	1 2				
32	Right Colic D3	1 2 3		e.g.Apical (right colic)		
13	Middle Colic D1	1 2				
23	Middle Colic D2	1 2				
33	Middle Colic D3	1 2		e.g.Apical node (middle colic)		

Station number	Vessel	Node	Estimate size of node (mm)	Comments e.g. Apical node	Colorimetric dyevisible Yes/No	Fluorescent Yes/no
41	Origin of SMA	1 2		Comment whether fluorescent (not excised)		
14	Left Colic D1	1				
24	Left Colic D2	1				
15	Sigmoid branche s D1	1 2				
25	Sigmoid Branche s D2	1 2				
16	Superior rectal D1	1				
26	IMA	1				
36	Origin of IMA	1		e.g.Apical node (IMA)		

Station number	Vessel	Node	Estimate size of node (mm)	Comments e.g. Apical node	Colorimetric dyevisible Yes/No	Fluorescent Yes/no
4	Any para- aortic nodes	1 2 3		Comment whether fluorescent (not excised)		
3 TOTAL	Any iliac nodes	1 2 3		Comment whether fluorescent (not excised)		
Additional Comments: Free text to add any additional areas of fluorescence – size, approximate location and whether excised as separate specimen.						

Table 1: Example of how to map the lymph nodes including the station number, vessel, number of nodes in each station, whether colorimetric dye was present, whether the node was fluorescent. Note that comments have been provided to identify the apical nodes (there may be more than one apical node if the tumour lies between two vascular ties). N.B. Right colic vessel may not be present - anatomy to be drawn in on Figure 2.

Figure 2. Right-sided resection. Modified Japanese staging subgroups.

To draw in vascular anatomy of right colic artery.

Figure 3. Left-sided resection.Modified Japanese staging subgroups.

To note any anomalies involving a left sided resection.

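### Each node's fluorescence is recorded as Yes/no with no definition of Yes and no planned grading or reading of the stored images, so the cut-off can differ between surgeons and between the sequential dose cohorts

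*Protocol*

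**What the plan says.** Protocol section 15.1 gives the primary endpoint as "Identification of the optimal dose for oral administration of 5-ALA for the accurate intraoperative detection of lymph node metastases". Section 8.1 sets the size of the comparison: "Initially two cohorts of 10 patients with positive lymph nodes (as verified on postoperative histology) will be treated with different doses of 5-ALA". The cohorts run one after the other, and the activity seen in the first decides which dose the second receives.

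The per-node reading is fixed by Table 1 of Appendix 4, where the column is headed "Fluorescent Yes/no". Its caption describes the content as "whether colorimetric dye was present, whether the node was fluorescent". The example table in Appendix 3 carries the same two-valued field into the pathology map. No section defines a fluorescent node, sets a background reference or asks for a second reading.

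Other records of fluorescence are kept. Appendix 4 states "Photos and videos will be taken via the laparoscopic stack to document areas of fluorescence" and "The settings of the Storz D-light laparoscopic system for 5-ALA fluorescence detection will also be documented". Section 13.4 lists "Details of D-Light 5-ALA lymph node assessment" among the operative data without saying what the details are. Section 15.2 makes "Optimisation and standardisation of fluorescence detection system" a secondary endpoint, so the detection system is still being worked out while the doses are compared.

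**The concern.** A visual Yes/no call depends on where the reader places the boundary. Here two surgeons at two centres place it, over successive cohorts, with a system whose settings may change. If the boundary moves between cohorts, a change in reading looks the same as an effect of dose. Both progression rules in section 8.1 use sensitivity alone, so a more generous *Yes* carries no penalty.

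With 10 informative patients per dose, a count of detections also ties fairly often, and a graded signal could separate doses that the count leaves level. CT nodes, by contrast, are graded from benign to malignant in Appendix 2.

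This is not a detail that an analysis plan can supply later. The proforma determines what surgeons write down in theatre, and an analysis plan cannot recover a grade that nobody recorded, except from images for which no reading is planned.

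**Working it through.** **1. The plan's own figure.** Section 8.1 links 2 detections in 10 to a 99% exact upper bound of at least 60%. The Clopper–Pearson upper bound is the 0.995 quantile of Beta(x+1, n−x). With n = 10:
- x = 1: 54.4%
- x = 2: 64.8%
- x = 3: 73.5%
- x = 4: 80.9%

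The stated rule reproduces, since 2 is the smallest count whose bound reaches 60%. For the later rule (bound at least 80%), 4 of 10 suffices if that stage has 10 node-positive patients. The point here does not dispute these figures.

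**2. Inputs for the rest.** From the Protocol: 10 node-positive patients per dose, two surgeons (section 9.4), sequential cohorts and a two-valued reading. Assumed, because the Protocol gives none of them: true detection rates per dose, a normal latent intensity with unit SD, one score per patient (the brightest node), and the size of any drift.

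**3. Ranking two doses with a stable cut-off.** Let p1 and p2 be the true detection rates. The latent shift is Φ⁻¹(p2) − Φ⁻¹(p1); for 60% v 80% this is 0.842 − 0.253 = 0.588 SD. *Yes* means intensity above the cut-off that gives p1 at the first dose. The four-level score adds cuts 0.7 SD below and above. The better dose is ranked first if it has the higher count, or the higher total score. Simulation with 200,000 replicates at 60% v 80%:

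| | Correct | Tie | Wrong | Correct, ties split |
|---|---|---|---|---|
| Yes/no count | 78% | 12% | 10.5% | 84% |
| 0–3 score | 86% | 4% | 9.7% | 88% |

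Correct ranking, count v score, over a range of assumed rates:
- 50% v 70%: 76% v 84%
- 70% v 90%: 81% v 91%
- 20% v 40%: 78% v 86%
- 20% v 60%: 96% v about 98.5%

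Most of the gain comes from resolving ties, and it shrinks when the doses differ widely.

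**4. What a moving cut-off could do.** If the cut-off loosens by s SD, a true rate p is read as Φ(Φ⁻¹(p) + s).
- p = 20%, s = 0.25: Φ(−0.842 + 0.25) = 28%. The chance of at least 2 of 10 rises from 62% to 81%.
- p = 20%, s = 0.5: Φ(−0.842 + 0.5) = 37%. The chance of at least 2 of 10 rises from 62% to 93%, and of at least 4 of 10 from 12% to 53%.
- Two doses both truly at 40%, s = 0.5 in cohort 2 only: cohort 2 is read as 60%. It looks better 75% of the time and cohort 1 looks better 13%. Without drift each looks better 41% of the time.

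**5. Whether the score alone cures drift.** Take 60% v 80% with a 0.5 SD looser reading in the cohort on the worse dose. Correct choice with ties split is 55% for the count and 57% for the score; wrong choice is 34% and about 38–39%. Adding levels does not help if all the boundaries move together. Written anchors and a separate reading of the images address that part.

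**The case against.** **Fluorescence is not recorded only as Yes/no.** A reader might infer that intensity is thrown away. The documents do not support this: images and device settings are kept, the operative form takes further unspecified details, and Table 1 is captioned as an example. Intensity could be graded afterwards. What stands is that no such grading or reading is planned.

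**Drift is not shown.** A reader might also infer that the cohort comparison is biased. Nothing in the Protocol shows that the boundary moves. Settings are logged, standardising the system is an aim, and the later progression analysis leaves out patients treated before the dose was chosen. That exclusion does not protect the initial comparison between doses, so the risk stays open there.

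**The count does not choose the dose alone.** Section 8.1 also brings in node-level data and practical considerations, toxicity is collected by dose, and the analysis is descriptive. Node-level data could break ties. This is a fair objection: counting every tie as a failure overstates the loss, and the ties-split figures are the fairer ones.

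**Intensity may not follow dose in this range.** The Introduction reports more tumour PpIX at a higher dose, but from one patient compared with two, at doses at or above the top of this trial's range. Section 8.1 mentions evidence that a lower dose is equally effective and says that fluorescence detection did not increase at higher doses. A graded score may therefore add less than the simulation suggests.

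**A binary endpoint suits the progression rules.** They ask whether a positive node was detected in a patient. That holds, and the endpoint should remain binary.

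**Conclusion.** The point holds in a limited form and is minor. The central reading of the index test has no written boundary, and the images that could check it have no planned reader. Two surgeons and sequential cohorts make that boundary matter for the primary endpoint.

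The benefit of grading is modest: about 84% v 88% correct choice with ties split at 60% v 80%, with wrong rankings almost unchanged. The drift figures show what would follow if the cut-off moved; they are not evidence that it will. All these figures depend on the assumed normal intensity, the assumed detection rates, one score per patient and the assumed size of drift. They do not support a claim that a Yes/no reading makes the dose choice unreliable, and no figure stated in the Protocol on this point is wrong.

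**What to change.** Before cohort 1:
- In Appendix 4 Table 1, replace the Yes/no column with an anchored score against adjacent normal mesentery: 0 none; 1 faint or doubtful; 2 clear; 3 as bright as or brighter than the primary tumour.
- State in advance which score counts as identified for both progression rules (2 or more would be a natural choice), and keep the binary per-patient endpoint for those rules.
- Reconcile what is counted per patient. The synopsis requires an identified node that is positive for tumour, whereas section 8.1 asks only for an identified node.
- Tabulate the scores by dose as supporting evidence for the dose choice.
- Have existing trial staff re-score the stored images against the same anchors, without sight of dose or histology, and report agreement with the theatre score.

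The cost is one form column, one descriptive table, a few seconds per node in theatre and the time to re-read images already being taken. The scale remains a visual judgement, so drift is reduced and made visible but not removed. The re-reading also covers only what was filmed or photographed.
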